1.2 Specific Aims

The specific aims of this proposal are to:

Aim 1: Introduce home-based targeted upper limb training in children with hemiplegia from ABI using a bimanual-to-unimanual training approach

We hypothesize that child-friendly home-based upper limb bimanual-to-unimanual training will lead to greater compliance and improved motor outcome on the Fugl Myer Scale compared to a conventional home training program.

Aim 2: Improve the understanding of the pattern of recovery of isolated joint movements in the pediatric population with hemiplegia following ABI.

We hypothesize that individuals receiving device-based bimanual-to-unimanual training will show improvement in active range of motion across upper limb joints compared with a conventional home training program.

This collaborative research will be performed in conjunction with the Motor Recovery Research Lab ([name]). The data obtained from this project will be used as preliminary data towards an NIH grant.

II. Study Design

Twenty children between the ages of 5-17 years with acquired brain injury 6 months to 2 years prior to enrollment will receive conventional home therapy (home exercise program) for 4 weeks followed by device-based home training for 4 weeks. We hope to recruit 10 children between the ages of 5-11 years and 10 children between the ages of 12-17 years. All enrolled children will complete the assessments below at baseline, after 4 weeks of conventional therapy, and after device training. The total length of study enrollment will be 8 weeks for all participants.

This is a pilot feasibility study hence sample size is small and arbitrary. Power analysis from these pilot data will be used to determine sample size in future studies. Subjects will be screened to ensure that they meet inclusion-exclusion criteria at Visit 1.

III. Subject Selection And Withdrawal

1. **Number of Subjects.**

Twenty (20) pediatric patients aged 5-17 years will be recruited. Subjects will be community dwelling individuals and will be voluntarily enrolled after obtaining the informed consent from their parent/guardian.

2. **Gender of Subjects.** There will be no gender bias for enrollment in the study

3. **Age of Subjects.** The age range of subjects is 5 -17 years

4. **Racial and Ethnic Origin.** There are no exclusions based on gender or ethnic group

5. **Inclusion Criteria**

1. Acquired Brain Injury at least 3 months prior to enrollment;
2. Unilateral hemiparesis

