Visit 2. Subjects will be assessed again 4 weeks after their home therapy program. At this visit they will also receive baseline testing and training on the device. After this visit, subjects will receive the device for training at home, which will be monitored on a weekly basis remotely by the occupational therapist to ensure compliance and to answer any questions.

Visit 3. This will be the post-device treatment assessment visit.

VI. Data Analysis & Data Monitoring

Data Analysis

Aim 1: Introduce home-based targeted upper limb training in children with hemiplegia from ABI using a bimanual-to-unimanual training approach. We will test the hypothesis that child-friendly home-based upper limb bimanual-to-unimanual training will lead to greater compliance and improved motor outcome on the Fugl-Meyer Scale, the Assisting Hand Assessment Test, active Range of Motion assessments, the Melbourne Assessment 2 and the PedsQL, compared to the conventional home training program. The groups will be compared using a two-way ANOVA.

Aim 2: Improve the understanding of the pattern of recovery of isolated joint movements in the pediatric population with hemiplegia following ABI. We will test the hypothesis that individuals receiving device-based bimanual-to-unimanual training will show improvement in active range of motion across upper limb joints compared with a conventional home training program.

The results of this study will pave the way for both understanding and meeting the needs of pediatric patients with Acquired Brain Injury in a systematic manner. Given the extent of plasticity in children there is a great need to rapidly optimize recovery so that physical, emotional and intellectual growth are as unhindered as possible. There is currently a dearth of evidence in how this can be accomplished. This study will provide pilot data for a larger study to optimize motor outcome pertaining to upper limb recovery as rapidly as possible.

Data Monitoring

The PI will be overall responsible for data monitoring.

(1) Types of Data or Events: All accumulated outcome data, enrollment numbers, reportable event data (including adverse reactions and unanticipated problems) and the overall compliance with the protocol will be monitored.

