Attending Physicians and Physical and Occupational therapists from the outpatient facility at New York University's Rusk Rehabilitation will refer patients with chronic stroke to the PI and study staff by giving them the PI's contact information if they meet study criteria.. Subjects who contact the PI and are found eligible for the study will be required to provide informed consent prior to participation in the study. The study protocol and informed consent forms will be approved by the IRB at NYU Medical Center. Subjects will be informed that they can discontinue the study or its procedures at any time, and that further evaluation or treatment will not be withheld. The identification and recruitment of subjects will protect the privacy of subjects and be free of undue influence.

2. Process of Consent

Assent will be obtained by the PI or HIPAA-certified delegates, in the PI's office, which is a private area, at the New York University's Rusk Rehabilitation, Hospital for Joint Diseases prior to participation in the study. The assent will be obtained jointly with the parent(s) and the minor. The assent document will be thoroughly discussed at a convenient time, free of time constraints and the subject and the parent will be given time to think about their decision. We will get the consent of the parent and the assent of the adolescent on the approved age-appropriate consent form. The subject and the

parent will be asked to provide a statement of their understanding of the procedures, risks, and a general concept of the study.

The parent (s) of the subject will be given a copy of both the consent and assent forms and be encouraged to contact the PI if they have further questions about the protocol. When the minor turns 18, we will get their consent (re-consent them). All subjects will also provide a separate consent for videotaping. The permission of only one parent will be required.

The subject (between the ages of 15-17 years old) will be asked to sign the assent form if they agree to participate in the study. The parent of the subject will be present at the time the document is signed along with the PI or her HIPAA-certified delegate

All subjects will also provide separate consent for videotaping of the clinical assessments. They will sign and date the Audio Video consent and will receive a copy of the signed consent. Videotapes of session and clinical assessments may be used for instruction and training purposes.

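### Apart from a between-condition test of compliance, this feasibility study plans no feasibility estimate or progression criterion, does not describe counting eligible families told of it, and would overstate compliance

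*Combined protocol and SAP*

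**What the plan says.** Section II gives the basis for the sample size: "This is a pilot feasibility study hence sample size is small and arbitrary". Section III.1 fixes the number: "Twenty (20) pediatric patients aged 5-17 years will be recruited". The use named for the results in section II is "Power analysis from these pilot data will be used to determine sample size in future studies". Sections 1.2 and VI add that the data are preliminary data for a grant application and for a larger study.

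The Data Analysis part of section VI has two hypotheses, both comparing device training with conventional training. Aim 1 is that device "training will lead to greater compliance and improved motor outcome on the Fugl-Meyer Scale" and on four further outcomes: the Assisting Hand Assessment, active range of motion, the Melbourne Assessment 2 and the PedsQL. The method is one sentence: "The groups will be compared using a two-way ANOVA". Aim 2 concerns active range of motion.

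Under Data Monitoring, the items to be watched include "All accumulated outcome data, enrollment numbers, reportable event data" and overall compliance with the protocol.

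On recruitment, section IX.1 has outpatient clinicians give patients the investigator's "contact information if they meet study criteria". The study then deals with those who make contact. Screening is at Visit 1, after consent (section V).

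Three other provisions bear on compliance. Section III.5 requires a history of compliance with home programmes. Section IV.2 drops children who are consistently below 80% of sessions. Section IX.5 removes a withdrawn subject's data at once.

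**The concern.** The feasibility label is what excuses an unsized sample, but the analysis does not follow from it. A team planning the larger trial needs to know what share of eligible families take part, what share finish each four-week phase, and how much of the prescribed training is done. The plan commits to none of these as an estimate with an interval, and it sets no value that would count for or against proceeding.

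Uptake is the most exposed of the three. A clinic tally that is not kept at the time cannot be reliably rebuilt afterwards.

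Compliance is the one feasibility-type outcome in the analysis, and it is exposed in another way. Followed as written, the rules on dropping and withdrawal take out the children who train least or leave, so the reported figure would look better than the experience of all enrolled children, and attrition could disappear from view.

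**Working it through.** **The plan's own figures.** The 20 children are declared arbitrary. No alpha, power, effect size, SD or precision target is given, so there is nothing to reproduce. The compliance rule can be checked: 5 sessions a week × 4 weeks = 20 sessions per phase, and missing 1 of 5 a week leaves 4/5 = 80%. It is internally consistent.

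**What 20 children can show on completion.** Exact (Clopper-Pearson) 95% limits for x of n are the 2.5% quantile of Beta(x, n − x + 1) and the 97.5% quantile of Beta(x + 1, n − x). The counts are illustrative.

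| Completing / enrolled | Estimate | Exact 95% CI |
|---|---|---|
| 16/20 | 80% | 56.3% to 94.3% |
| 18/20 | 90% | 68.3% to 98.8% |
| 20/20 | 100% | 83.2% to 100% |

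A progression rule is also workable at this size. With assumed true completion rates, a rule to proceed if at least 16 of 20 complete has a 5.1% chance of being met when the true rate is 60% and an 83.0% chance when it is 85% (exact binomial).

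**Uptake.** Uptake = enrolled / eligible children told. The numerator is 20; the denominator is not in the documents. For assumed pools of 25, 40, 80 or 200, uptake is 20/25 = 80%, 20/40 = 50%, 20/80 = 25% or 20/200 = 10%. Nothing the protocol says it will record separates these cases.

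**Direction and possible size of the compliance bias.** If the section IV.2 rule is applied, each child who stays has done at least 80% of sessions, that is 0.80 × 20 = 16 per phase. Mean compliance among children who stay is then at least about 80%, whatever the training is like. Suppose 16 of 20 stay and each does exactly 16 sessions.

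- Among those who stay: (16 × 16) / (16 × 20) = 256/320 = 80%.
- Over all enrolled, if the other four did none (the extreme case): 256 / (20 × 20) = 256/400 = 64%.

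The true gap depends on how many leave and how much they did first. Its direction does not, provided those who leave did less than those who stay. The compliance contrast also has unequal measurement: logs alone in the conventional phase, logs plus remote monitoring in the device phase.

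**What 20 children can show by a test.** For a two-sided 5% paired t-test, the critical value on 19 df is 2.093 and the noncentrality is d√n. No effect size is stated, so a range is assumed.

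| Assumed d (SD of paired differences) | d√20 | Power |
|---|---|---|
| 0.3 | 1.34 | 25% |
| 0.5 | 2.24 | 56% |
| 0.8 | 3.58 | 92% |

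The paired t-test stands in for the stated two-way ANOVA, whose factors are not given; each child has both treatments, so the within-child contrast is the relevant one.

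**The planned power analysis.** The 95% limits for an SD from n = 20 are s√(19/χ²), with the χ² quantiles on 19 df: 0.76s to 1.46s. Sample size goes with the square of the SD, so a future sample size based on it could be off by a factor of 0.58 to 2.13.

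**The case against.** A reader might infer that the study analyses efficacy alone. The documents do not support that: Aim 1 names greater compliance, in section 1.2 and again in section VI, and compliance with home training is a feasibility outcome. It is, however, tested as a difference between conditions and not estimated against a planning value. The 80% figure in section IV.2 is a rule for individual children, not a criterion for the study.

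A reader might also infer that the study cannot show whether a larger trial is feasible, or that its recruitment denominator is lost. Both go too far. Enrolment and compliance are monitored, so completion could be calculated if records of all enrolled children are kept. The steps from contact to consent and from consent to eligibility can be counted too. Only the step from being told to making contact is unseen, and that rests on silence: section IX.1 neither describes nor rules out a referral log. One passage of the document was also unavailable for this review.

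It is fair to add that estimating variability for a future power calculation is a legitimate pilot aim and needs the outcome data. That stands, and it argues for reporting estimates with their imprecision. Nothing in the protocol says a non-significant result would be taken as showing no benefit; the power figures show only how little such a result could say at small to moderate effects.

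**Conclusion.** The point holds as a matter the sponsor should correct before enrolment. Outside a comparative test of compliance, the supplied text specifies no feasibility estimate and no progression criterion, and the referral route as described does not capture how many eligible families were told. Compliance as planned would be biased upward and attrition obscured, unless dropped and withdrawn children stay in the denominator.

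On size: completion can be estimated to roughly 56% to 94% around 80%. Uptake could lie anywhere from 10% to 80% across the assumed pools. Power runs from about 25% to 92% across the assumed effects.

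The conclusion rests on reading silence about a referral log as absence, on the compliance rule being applied as written, and on section IX.5 being applied to withdrawn children's session records. Whether a child dropped for low compliance counts as withdrawn is not stated. The eligible pools, completion rates and effect sizes are illustrative assumptions.

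**What to change.** 1. Have referring clinicians keep a tally, without identifiers, of each child given the study contact details.
2. In section VI, name feasibility as an objective and report with exact 95% CIs: enrolled / eligible children told, and children completing each phase / all enrolled.
3. Report sessions done / 20 prescribed in each phase over all enrolled children. Keep at least an anonymous count of those dropped or withdrawn, and say how section IX.5 applies to it. This concerns counting only; the rule on dropping children is not in question here.
4. State a progression value for each figure before first enrolment.
5. Report the outcome contrasts as estimates with 95% CIs, and do not conclude benefit or no benefit from a p-value.

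The cost is a clinic tally sheet and some wording. No visit, assessment or treatment changes. The downside is giving up a significance claim that the study was not sized to support.

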3. History of compliance with home exercise programs in the past.

6. **Exclusion Criteria**

1. Any social or medical problem that precludes compliance with the protocol
2. Comorbid seizure disorder or other neurological disease
3. Treatment with botulinum toxin or intrathecal baclofen in the 3 months preceding enrollment
4. Implanted neuromodulatory or electronic device or other complicating illness
5. Lack of capacity to consent

7. **Vulnerable Subjects**

The patients meeting inclusion criteria will be children. We will only enroll patients with capacity to provide informed consent. We will provide information to the subjects in terms that they can fully understand, and capacity to consent will be determined by the subject's verbal understanding of the protocol as determined by the PI. We will not exert any overt or covert coercion, and no financial incentive will be offered. The consent document that the subject will be asked to sign will be written in the language that the potential subject understands and will be approved by the IRB.

IV. Study Device

IV.1 **Description**

The device is a FDA Class I exempt medical device, and is registered with the FDA

(<http://www.accessdata.fda.gov/scripts/cdrh/cfdocs/cfRL/rl.cfm?lid=461627&lpcd=PKS>). The device facilitates movements of the affected hemiparetic arm by moving the unaffected arm at the shoulder and elbow joint. The device is interfaced with a video game for motivation and feedback. It also facilitates movements of the forearm and grasp and release on both the affected and unaffected sides (**Fig. 1**).

Fig.1. Bimanual Arm Trainer

Training Protocol:

The home-based training protocols both with and without the device will be consistent with the fundamental principles of neurorehabilitation as outlined by Bobath (Bobath 1978) and with motor learning principles (Shepherd and Carr 2006). The main postulates of the Bobath concept are that (1) posture and movement are not separate entities, (2) sensory input influences motor output and (3) muscle strength is a does not necessarily equal function (Vaughan-Graham, Cott et al. 2014). The principles of motor learning are repetitive task-specific practice with feedback (Bosse, Mohr et al. 2015)

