Fig.3. Training a child with the Bimanual Arm Trainer

Conventional non-device based home training will be provided using a home-exercise program provided by an occupational therapist and customized to the

patient's needs using the principles from Bobath and Motor Learning. Patients will also be asked to train specific movements repeatedly for *45 minutes five days a week* for 4 weeks and compliance will be monitored through training logs.

Progression of training: Patients with spastic paresis (Brunnstrom's stages I and II) will engage in bimanual-to-unimanual training (**Fig. 4**) with rhythmic auditory stimulation initially, those with spastic co-contraction (Brunnstrom's stages III and IV) will engage in bimanual-to-unimanual training without rhythmic auditory stimulation (Aluru, Lu et al. 2014). At each weekly review of the previous week's data,

the therapist will determine the conditions of further training. Training will be progressed as per standard practice in individuals receiving standard home training by a pediatric occupational therapist.

Fig. 4. Example of protocol for bimanual-to-unimanual training within a training session. The left arm (red box) was affected.

IV.2 Subject Compliance Monitoring

The study Occupational Therapist (OT) will monitor compliance with the training protocol with training logs provided to the child and parents. The OT will also review the training data and determine adherence to the treatment regimen. If subjects are consistently non-compliant and demonstrate less than 80% compliance with the training sessions (i.e., miss more than 1 training session per week), they will be dropped from the study.

V. Study Procedures

All data will be obtained solely for research purposes.

Visit 1. Subjects will provide informed consent and be screened to ensure that they meet inclusion-exclusion criteria. If they meet criteria, they will undergo further assessments using the Fugl-Meyer Scale, the Assisting Hand Assessment Test, the Melbourne Assessment 2 and the PedsQL (see attached scales). Total testing time will not exceed three hours, and the subjects will be given adequate rest breaks to ensure that they do not become fatigued. All subjects will be given a home exercise program and exercise logs to record the time spent in training at home.

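### Section IV.2 drops poor compliers from a study that tests compliance, so the conventional-versus-device comparison is selected on its own outcome, in a direction the plan leaves open

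*Combined protocol and SAP*

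**What the plan says.** - **Compliance is an outcome.** Section VI, Aim 1, tests the hypothesis that device training "will lead to greater compliance and improved motor outcome on the Fugl-Meyer Scale" and other scales, against the conventional program. Section 1.2 states the same hypothesis. Compliance is named first.
- **The order is fixed.** Section II gives every child "conventional home therapy (home exercise program) for 4 weeks followed by device-based home training for 4 weeks".
- **Poor compliers are removed.** Section IV.2 begins "If subjects are consistently non-compliant and demonstrate less than 80% compliance" and continues "less than 80% compliance with the training sessions (i.e., miss more than 1 training session per week), they will be dropped from the study". The rule is not limited to one phase, and 'consistently' is given no number of weeks.
- **Completion is stated for everyone.** Section II: "All enrolled children will complete the assessments below at baseline, after 4 weeks of conventional therapy, and after device training". It also puts enrollment at 8 weeks for every participant.
- **The analysis is one sentence.** Section VI: "The groups will be compared using a two-way ANOVA". No analysis set is named, and nothing is said about children who were dropped.
- **Entry already selects on compliance.** Section III.5 requires "History of compliance with home exercise programs in the past", and Section III.6 excludes problems that would prevent compliance.
- **Data removal.** Section IX.5 removes the data of a subject who withdraws. It is written for voluntary withdrawal and does not mention children dropped under IV.2.

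**The concern.** Whether a child supplies device-phase compliance depends on that child's conventional-phase compliance, which is one side of the comparison being tested. Keeping every log does not cure this, because device-phase sessions of a child dropped in phase 1 never take place. The motor comparison after the device has a related problem. It would rest on children who kept up training, yet the plan does not label it so, and Section VI says "This study will provide pilot data for a larger study to optimize motor outcome". A reader planning that larger study would want to know how many children fell below 80%, in which phase, and what happened to them.

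**Working it through.** **Step 1: the plan's own threshold.** Both programs run five days a week for 4 weeks (Section IV), so 5 x 4 = 20 sessions per phase. One missed session a week is 4/5 = 80% and two is 3/5 = 60%. Missing more than one a week is therefore the same as falling below 80%, and the figure reproduces.

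**Step 2: who supplies which data under IV.2 as written.**

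| Child | Phase 1 compliance | Device-phase compliance | Visit 3 |
|---|---|---|---|
| Dropped in phase 1 | up to the drop | none | none |
| Dropped in phase 2 | full | up to the drop | none |
| Not dropped | full | full | yes |

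**Step 3: direction.** It depends on who is analysed.
- *Entrants, paired (children who reach the device phase).* They were selected for high phase 1 values, partly by chance. Phase 2 falls back towards each child's own level, so the comparison leans against the device.
- *All phase 1 logs against phase 2 entrants.* Phase 2 lacks the poorer compliers, so the comparison leans for the device.
- *Completers of both phases.* Both means are pushed up and a true difference shrinks. This applies only if the logs of phase 2 drops are left out, which the plan does not say.

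**Step 4: size, as an illustration.** The documents give no attendance figures, so the inputs are assumptions. Each week is binomial(5, p) for 4 weeks per phase. Child-level p is logit-normal with SD 1, with between-phase correlation 0.6. There are 1,000,000 simulated children per scenario. 'Consistently' is read as below 80% in at least 3 of 4 weeks, or in all 4; ranges run from the first reading to the second. Differences are device minus conventional, in percentage points.

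| Conventional / device attendance | True difference | Phase 1 drops of 20 | Entrants, paired | Completers | All phase 1 logs vs entrants |
|---|---|---|---|---|---|
| 90% / 95% | +5 | 0.7 to 0.2 | +4.0 to +4.6 | +4.1 to +4.7 | +5.3 to +5.1 |
| 85% / 90% | +5 | 1.8 to 0.6 | +2.8 to +4.1 | +3.5 to +4.3 | +6.0 to +5.4 |
| 75% / 85% | +10 | 4.9 to 2.2 | +4.2 to +7.0 | +5.7 to +7.6 | +12.7 to +11.5 |

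Loss at 75% / 85% in entrants: (10 - 4.2)/10 = 58%, to (10 - 7.0)/10 = 30%.

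With no true difference, entrants show -0.9 to -0.3 at 90%, -1.9 to -0.8 at 85% and -4.7 to -2.5 at 75%; completers show 0. The standard error of the entrant comparison with 20 enrolled (SD of the within-child difference divided by the square root of the number of entrants) is about 2.6 to 2.7 at 90% and about 4.3 at 75%.

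**Step 5: sensitivity.** With correlation 0.3 to 0.8, SD 0.5 to 1.5 and both readings, entrants show +0.1 to +9.0 of a true +10 at 75% / 85%. With no true difference they show -2.4 to 0.0 at 90% and -9.2 to -0.9 at 75%. The size is thus largely set by the assumptions.

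**Step 6: does a model that keeps all phase 1 logs help?** Regressing device-phase on phase 1 compliance in entrants, then averaging over all enrolled children, returned +10.1 (true +10), +5.0 (true +5) and -0.3 to 0.0 (true 0). This assumes full phase 1 logs and drops that depend only on recorded phase 1 sessions.

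**The case against.** **The bias may be small.** Children are chosen for past compliance. At 90% in both phases the null bias is under 1 point, well below the standard error, and the chance that nobody is dropped in phase 1 is about 47% to 81%. It matches the standard error only near 75%, which is low for children screened in this way. This stands. However, the plan gives no attendance figure and foresees poor compliance enough to write a removal rule. At 85% the chance of at least one phase 1 drop is already about 47% to 85%.

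**Section II is only a schedule.** A reader might infer a flat contradiction between Section II and IV.2. The documents do not compel that reading: the sentence can be taken as the planned visit schedule, and read literally it would clash with voluntary withdrawal as well. The two passages need reconciling, and no more is claimed.

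**Analysing all enrolled children is not always right.** A reader might conclude that all enrolled children must be the main set whatever happens. In a single-sequence design, a child dropped in phase 1 who never receives the device has no device-phase compliance and no true post-device assessment. Counting a later visit as post-device would mix non-exposure into the device result. This objection stands, and the fix is conditional for that reason.

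**It is a pilot.** Section II calls the sample size arbitrary. A motor estimate in completers is a legitimate choice if labelled as such; the plan does not label it.

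**Conclusion.** The point holds and should be fixed. As written, IV.2 selects the compliance comparison on its own outcome and limits the motor result to children who kept up training. Confidence is high for this mechanism only.

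The direction is not fixed. A reader might infer that the rule works against the device, or for it; either follows only after choosing an analysis set, and the plan names none. The size cannot be derived from the documents. Under the assumptions in the working it runs from under 1 point (null case, 90%) to a loss of 30% to 58% of a true 10-point difference (75% against 85%, entrants).

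Two further inferences are not supported. One is that dropped children's data will be deleted: IX.5 is written for voluntary withdrawal and is silent on IV.2. The other is that the future sample size will be wrong. In the illustration at 75% / 85% the standardised paired compliance effect is 0.55 in all children and 0.46 to 0.51 in completers, because a smaller SD partly offsets the smaller difference.

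**What to change.** 1. Reword IV.2 so that non-compliance does not end study follow-up. Keep all compliance data collected, count compliance below 80% as an outcome, and carry out the remaining scheduled assessments where the family agrees. Reconcile the wording with Section II.
2. Report the number below 80% and the number dropped in each phase.
3. The sponsor must decide and state whether a child who is non-compliant in phase 1 goes on to the device phase.
   - *If such children go on:* analyse all enrolled children as the main set. Add a labelled per-protocol analysis with the 80% cut-off and 'consistently' defined.
   - *If they do not:* do not treat their later assessment as post-device. Analyse device-phase entrants and limit the compliance and motor conclusions to children who complied with conventional training. Support the compliance comparison with a model that keeps all phase 1 logs, for example a likelihood-based mixed model of both phases. State its assumption that drops depend only on recorded phase 1 sessions.
4. State that the IX.5 data removal does not apply to children dropped under IV.2 unless they withdraw.
5. State the remaining limits. The fix removes the selection only. Fixed order and different monitoring (logs alone in the conventional phase, logs plus remote monitoring in the device phase) still confound the compliance contrast.

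**Cost.** Protocol and consent wording, and visits that are already scheduled, for children who would have been dropped in either phase. In the illustration these number 0.2 to 0.8 of 20 at 90% / 95%, 0.8 to 2.3 at 85% / 90% and 2.6 to 5.7 at 75% / 85%. The average effect may look smaller once poor compliers are included.
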